9.3 Selection of study population

9.3.1 Recruitment

The study site will recruit subjects from the greater Baltimore, Washington DC and surrounding regions.

IRB approved advertising will be conducted utilizing a wide range of print, electronic, audio, video and/or social media. Subjects responding to the advertisements by a phone call or through the website will be pre-screened for eligibility based on a standard pre-screening questionnaire administered by a CIR recruiter. Some elements of the inclusion/exclusion criteria will be

discussed with the subject at that time and a preliminary assessment will be made regarding the individual's eligibility for study participation.

9.3.2 Compensation for participation

Compensation will occur as detailed below. Compensation will be provided only for completed study procedures designated for compensatory payment. If a participant is eligible to participate in the investigational protocol after screening, and completes all study visits, procedures and follows all the rules, they will receive a total of \$3,860.

Volunteers that present to the unit as an alternate, but are not admitted, will receive \$200 for screening and \$200 for presenting to the unit (a total of \$400). Volunteers who are admitted to the unit overnight, but are discharged prior to challenge, will receive \$200 for screening (if not already received) and \$350 for staying on the inpatient unit overnight.

If a participant is not eligible for discharge by Day 9 because of illness or not having 2 consecutive negative stool culture results they will receive \$350 per additional inpatient day.

9.3.3 Screening according to protocol CIR200

Initial in-person screenings will be conducted under a separate, IRB-Approved general screening protocol ("Screening of adult volunteers for eligibility to participate in clinical studies evaluating investigational vaccines, antimicrobial agents, other disease prevention measures or the pathogenesis of infectious agents" CIR 200, JHSPH IRB 00010083). Subjects will be made aware that the screening process may take several visits to complete.

Using this screening protocol, a medical history/physical exam and a series of clinical laboratory tests may be completed to rule out occult illness and pregnancy. These laboratory tests may include, but are not limited to, complete blood count (CBC), serum chemistries, hepatitis B antigen, hepatitis C antibody, HIV-1 antibody, IgA levels, serum hCG (for people of childbearing potential), and urine toxicology (drug screening). (Confirmatory testing will be performed on participants who test positive for hepatitis C or HIV-1 antigens.) Participants who have \leq 2 mild (grade 1) non-hematologic abnormalities may be included if the PI determines that their participation will not present undue risk to the participant. Participants with $>$ 2 mild abnormalities will not be included in the study. Participants with clinical laboratory abnormalities of greater than mild severity will not participate in this clinical trial. The clinical toxicity grading scale that will be used as a guideline is based on the scale used by the Division of AIDS (DAIDS) for adverse events and the guidance from the US Food and Drug Administration (FDA) Center for Biologics Evaluation and Research. If any additional safety labs are performed, either scale may be utilized.

Participants who are eligible after completing the general screening assessment may be asked to complete study-specific screening under this protocol.

9.3.4 Number of subjects

Up to 30 (minimum 25) healthy subjects will be enrolled in the study. Since there is a maximum capacity of 30 subjects for the in-patient period, the number of subjects who receive the

Confidential

28 (67)

Template Version:30MAR2020

(App 1 SOP EtC1011)

E24377A strain will not exceed 30; however, additional alternate subjects may be recruited to fill in for subjects who are ineligible or chose to leave prior to challenge receipt.

9.3.5 Screening and enrollment log

The clinic will keep a log of all subjects screened and enrolled. The reason for screen failure should be stated for all subjects screened but not enrolled. The reason for withdrawal should be stated for all subjects enrolled but not completed.

Subjects who have signed the CIR200 ICF will be assigned a CIR200 screening number. Subjects who sign the study specific consent form will be assigned a study specific subject number.

9.3.6 Inclusion criteria

For inclusion in the study, subjects must fulfil all the following criteria:

1. Healthy adults between 18 and 50 years of age, inclusive, at the time of signing the informed consent.
2. General good health, without clinically significant medical history, physical examination findings or clinical laboratory abnormalities per clinical judgment of PI.
3. Negative pregnancy test at screening and prior to challenge for people of childbearing potential. People of childbearing potential must agree to use an efficacious hormonal or barrier method of birth control during the study. Abstinence is acceptable. People of childbearing potential unable to bear children must have this documented (e.g. tubal ligation or hysterectomy) or must have negative pregnancy tests at screening and prior to challenge.
4. Willingness to participate in the study after all aspects of the protocol have been explained and written informed consent obtained.
5. Completion of a training session and demonstrated comprehension of the protocol procedures and knowledge of ETEC associated illness by passing a written examination (70% pass score).
6. Availability for the study duration, including planned follow-up visit/contact.

9.3.7 Exclusion criteria

Subjects must not enter the study if any of the following exclusion criteria are fulfilled:

1. Presence of a significant medical or psychiatric condition which in the opinion of the investigator precludes participation in the study, including gastrointestinal disease (gastritis, irritable bowel disease as suggested by Rome III criteria or medical diagnosis, inflammatory bowel disease). Some medical conditions which are adequately treated and stable would not preclude entry into the study. These conditions might include stable asthma controlled with inhalers or mild hypertension stably controlled.
2. Significant abnormalities in screening haematology, or serum chemistry as determined by PI.
3. Presence in the serum of HIV antibody, HbsAg, or HCV antibody with confirmation of infection (e.g. by HCV PCR).
4. Evidence of IgA deficiency (serum IgA < 7 mg/dl or limit of detection of assay).

5. Evidence of current alcohol or drug dependence.
6. Subjects whose Body Mass Index (BMI) is less than 19.0 or greater than 37.0 (kg/m²).
7. Recent vaccination or receipt of an investigational product (within 30 days before challenge) or intended vaccination or receipt of investigational products until 60 days after challenge, with the exception of licensed vaccine for influenza or SARS-CoV-2 vaccination that may be given up to 7 days prior to challenge.
8. Positive test for SARS-CoV-2 at arrival to the unit on the day of in-patient admission.
9. Intention to donate blood or blood products within one month following the completion of study participation (note: The Red Cross will not allow blood donations for 1 year following participation in an investigational research study).
10. Any other criteria which, in the investigator's opinion, would compromise the ability of the subject to participate in the study, the safety of the study, or the results of the study.
11. Abnormal stool pattern (fewer than 3 per week or more than 3 per day).
12. Regular (\geq weekly) use of laxatives, antacids, or other agents to lower stomach acidity.
13. Use of any medication known to affect the immune function (e.g., corticosteroids and others) within 30 days preceding the challenge or planned use during the active study period. Use of inhaled or topical steroids may be permitted per PI discretion.
14. History of microbiologically confirmed ETEC infection in the last 3 years.
15. Occupational handling of ETEC currently, or in the past 3 years.
16. Travel to countries where ETEC infection is endemic (most of the developing world) within two years prior to dosing OR visit for $>$ two months in ETEC endemic countries during the last 10 years, OR planned travel to endemic countries prior to study day 180.
17. Vaccination for or ingestion of ETEC, cholera, or LT toxin within 5 years prior to dosing.
18. Use of antibiotics during the 14 days before challenge dosing or proton pump inhibitors, H2 blockers or antacids within 48 hours prior to challenge dosing.
19. History of diarrhea in the 7 days prior to challenge (outpatient diarrhea is defined as \geq 3 unformed (grade 3 or greater) loose stools in 24 hours).
20. Known allergy to two of the three following antibiotics: ciprofloxacin, amoxicillin, and/or azithromycin.

9.3.8 Removal of subjects from therapy or assessment

Subjects are free to discontinue their participation in the study at any time and for whatever reason without affecting their right to an appropriate follow-up investigation or their future care.

Subjects may be discontinued from the study at any time at the discretion of the Investigator for any of the following reasons:

- Severe non-compliance to the CSP procedures, as judged by the Investigator and/or SBH
- Subject is lost to follow-up (at least 3 attempts will be made to contact them, then a certified letter will be sent to their last known address)
- Significant AEs posing a risk for the subject, as judged by the Investigator and/or SBH

The primary reason for withdrawal / discontinuation must be specified in the eCRF and medical records.

After administration of E24377A, the subject will be encouraged to remain in the in-patient unit for the protocol-specified period (i.e., until they meet discharge criteria of 2 stools negative for challenge; see Section 9.4.8.2) and return for the scheduled out-patient study site visit on Day 29, and be available for a final contact by phone approximately 6 months after challenge. Furthermore, subjects will be encouraged to take the full course of antibiotics in order to reduce the risk of secondary infection after discharge.

If a subject expresses interest in withdrawing from the study after E24377A administration but before completion of the in-patient period, then the subject will be started on antibiotic therapy and encouraged to remain in the in-patient unit until they are no longer infected, as determined by negative stool culture. If the participant is amendable to returning for any or all in-person outpatient visits, they will be considered “off treatment” but not terminated from the study.

However, if the subject elects to withdraw from the study immediately, then the subject will receive a single dose of ciprofloxacin 500 mg prior to discharge from the in-patient unit and be provided with the remaining 5 doses of ciprofloxacin 500 mg twice daily (BID). They will be encouraged to bring stools samples in to ensure clearance of the challenge organism.

If a subject terminates the study before Day 29, every effort will be made to have the subject undergo the procedures as described in Section 9.5.6.4 for the follow-up visit.

In case an early termination visit as described above is not possible, a follow-up safety phone call should be made as soon as possible after termination to capture any SAEs or AESIs since the last study visit, if possible.

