7.3.2 Risks

Risks Associated with ETEC Infection: The main risk is also the primary objective in this study: diarrhea caused by ETEC. Infection with ETEC can cause profuse watery diarrhea, abdominal cramping, abdominal pain, malaise, headache, urgency of defecation, lightheadedness and/or dehydration. Fever, nausea with or without vomiting, chills, loss of appetite, muscle aches and bloating can also occur but are less common. Illness develops 1-3 days after exposure and usually lasts 3-4 days [29] without treatment, but generally improves within 24 hours of antibiotic therapy.

In order to reduce the risk of secondary infection after discharge, all subjects in the study will receive a 3-day course of antibiotics starting no later than Day 6. Ciprofloxacin is the first-line antibiotic treatment for all subjects. If a subject is unable or unwilling to take ciprofloxacin, azithromycin or amoxicillin will be used instead. The risk of diarrhea complications will be minimized by a conservative approach to timing of antibiotic administration, well within an interval that has been shown to be efficacious, as well as daily clinical monitoring. Stool output will be closely monitored.

Risks Associated with Post-Infectious Irritable Bowel Syndrome (PI-IBS): Recent studies also suggest an increased risk of post-infectious irritable bowel syndrome (PI-IBS) following bacterial enteritis, and infection with ETEC has been found to be associated with these sequelae. A long duration (>2 weeks) of TD has been shown to be a risk factor for development of PI-IBS [30]. Prompt treatment of the ETEC infection, as done in the present study, cuts the duration of

any ETEC illness short and thus most likely eliminates the risk of PI-IBS. Symptoms of PI-IBS will be screened for with the Functional Bowel Disorder Survey (FBS) administered on study day 180. A study provider will review each FBS. Any participant identified as having a risk for PI-IBS will be referred for follow-up care. PI-IBS may be detected in 3-17% of people who experience travelers diarrhea (TD) [9], however there have been no documented cases of PI-IBS in enteric challenge study participants [31].

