9.4.8.2 Concomitant therapy during the study

During the study, all subjects will receive a 3-day course of antibiotics.

On the morning of Day 6 (or sooner if the subject met the criteria for early antibiotic treatment; see below), all subjects will start a 3-day course of ciprofloxacin 500 mg BID.

Subjects with an allergy to or who are unwilling to take a fluoroquinolone, may receive azithromycin 500 mg by mouth daily for three days or amoxicillin 500 mg by mouth three times daily for three days.

If, because of illness, a subject is unable to take oral antibiotics, intravenous antibiotics may be given at an appropriate dose based on weight and clinical status.

Criteria for early antibiotic treatment

Subjects meeting any of the following criteria before Day 6 will start antibiotic treatment at that time:

- Severe diarrhea as defined as >800 grams of grade 3-5 stools within a rolling 24 hour-period (see Section 9.5.3.1.2).
- Stool output consistent with moderate diarrhea for 48 hours
- Diarrhea of any severity AND 2 or more of the following symptoms: severe abdominal pain, severe abdominal cramps, severe nausea, severe headache, severe myalgias, severe arthralgia), any fever ($\geq 100.4^{\circ}\text{F}$, 38.0°C), or any vomiting
- Any fever $\geq 102.1^{\circ}\text{F}$ (39.0°C)
- A study clinician determines early treatment is warranted for any other reason

Subjects who meet the criteria for early antibiotic treatment, may be discharged from the in-patient unit earlier than anticipated upon meeting discharge criteria. Discharge criteria include at least 2 stools negative for the challenge organism, having taken at least 2 doses of antibiotics, and have no or improved symptoms.

Subjects taking any other non-antibiotic medication on a chronic basis may continue with that medication unless directed otherwise by a study clinician. All such medication will be collected on admission to the inpatient facility and will be dispensed by study staff until discharge.

Rehydration

Subjects passing grade 3-5 stools post-challenge will be asked to drink liquids, at the same volume as their stool output.

A subject may be administered IV fluids if they:

- Experience abrupt onset of diarrhea, defined as passage of an initial loose/liquid stool of >300 g, or >400 g of loose/liquid stools over 2 hours in conjunction with other symptoms, as determined by PI or designee.

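### For subjects who leave the unit at once after withdrawing, Section 9.3.8 names ciprofloxacin only, which conflicts with the protocol's own alternatives for eligible subjects who are allergic to it or unwilling to take it

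*Protocol*

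**What the plan says.** Protocol Section 9.3.8 treats withdrawal after challenge, but before the in-patient period is complete, in two branches.

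- A subject who wants to withdraw but may still be persuaded to stay: "then the subject will be started on antibiotic therapy and encouraged to remain in the in-patient unit". No drug is named.
- A subject who chooses to leave at once: "the subject will receive a single dose of ciprofloxacin 500 mg prior to discharge from the in-patient unit". The same sentence supplies the other 5 doses of the twice-daily course, again as ciprofloxacin. It has no exception for allergy or refusal. The section's one reference to Section 9.4.8.2 concerns discharge criteria, not the choice of antibiotic.

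Exclusion 20 in Section 9.3.7, repeated in the synopsis, reads "Known allergy to two of the three following antibiotics: ciprofloxacin, amoxicillin, and/or azithromycin".

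Section 9.4.8.2 sets the default, "all subjects will start a 3-day course of ciprofloxacin 500 mg BID", and follows it with an alternative: "Subjects with an allergy to or who are unwilling to take a fluoroquinolone, may receive azithromycin 500 mg by mouth daily for three days". The other option named there is amoxicillin. Section 7.3.2 is firmer: "If a subject is unable or unwilling to take ciprofloxacin, azithromycin or amoxicillin will be used instead". The synopsis, the overall design description in Section 9 and SAP Section 2.1 also list the alternatives for allergy. All of these places except the synopsis extend them to subjects who are unwilling. The SAP does not address the withdrawal rule.

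**The concern.** A volunteer whose only antibiotic allergy is to ciprofloxacin passes exclusion 20 and can be challenged. The protocol expects such people, because it writes a route for them in several places. The one paragraph written specifically for immediate departure does not carry that route.

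For an allergic subject, following that paragraph literally means one dose of a drug to which the subject is known to react, given just before leaving the staffed unit, and five more to take at home. Section 7.3.2 acknowledges that allergic reactions to the study antibiotics occur, though rarely. For an unwilling subject the issue is different: nothing compels ingestion, but the subject may leave without a course that he or she will take. That works against the protocol's stated reason for treating everyone, which is to lower the risk of secondary infection after discharge.

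**Working it through.** This is a check of text against text. The only arithmetic is a dose count.

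**Step 1. Can an affected subject be enrolled?** Exclusion 20 requires allergy to two of three drugs. Allergy to ciprofloxacin alone is one of three, so the criterion is not met and the volunteer remains eligible. Unwillingness to take ciprofloxacin is not an exclusion.

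**Step 2. What does each place prescribe for that subject?**

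| Place | Situation covered | Allergic to ciprofloxacin | Unwilling to take it |
|---|---|---|---|
| Protocol 7.3.2 | all subjects | alternative (as unable), mandatory wording | alternative, mandatory wording |
| Protocol 9.4.8.2 | course during the study | alternative, permissive wording | alternative, permissive wording |
| Protocol 9, design description; SAP 2.1 | course during the study | alternative | alternative |
| Protocol synopsis | course during the study | alternative | not mentioned |
| Protocol 9.3.8, subject stays on the unit | withdrawal under discussion | drug not named | drug not named |
| Protocol 9.3.8, subject leaves at once | immediate withdrawal | ciprofloxacin | ciprofloxacin |

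The last row is the only one that names ciprofloxacin without offering an alternative. The sharpest conflict is with Section 7.3.2, since both sentences are mandatory: one says that another drug is used, the other that ciprofloxacin is given.

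**Step 3. Could ciprofloxacin in Section 9.3.8 be shorthand for whichever course applies?** Count the doses.

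- Section 9.3.8: 1 before departure + 5 to take home = 6.
- Ciprofloxacin in Section 9.4.8.2: 2 per day × 3 days = 6.
- Azithromycin in Section 9.4.8.2: 1 per day × 3 days = 3.
- Amoxicillin in Section 9.4.8.2: 3 per day × 3 days = 9.

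The total of 6 matches ciprofloxacin and neither alternative. The rule was written for ciprofloxacin alone. The drug-neutral wording of the other branch in the same section points the same way.

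**Step 4. Does it touch the analysis?** The full analysis set (Protocol 9.7.5.1, SAP 3.3) is every challenged subject with available data. Which antibiotic a subject is given on leaving changes neither membership of that set nor the stools already recorded. The primary proportion, its Clopper-Pearson interval and the planned number of subjects (up to 30, minimum 25) are unaffected.

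**The case against.** The best answer is that the protocol should be read as a whole. Section 7.3.2 is not limited to subjects who complete the stay, and Section 9.4.8.2 opens by covering all subjects during the study. Section 9.4.8.2 also states its ciprofloxacin default in unconditional form and gives the exception in the next sentence. On this reading, Section 9.3.8 repeats the default and merely fails to repeat the exception. It nowhere says that ciprofloxacin is to be given despite a known allergy. Eligibility is reviewed at screening, on Day -1 and on Day 1, and the unit has medical staff around the clock, so an allergy would probably be known and acted on.

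Much of this stands, and it lowers the likelihood of harm. It does not remove the conflict. A safe outcome would depend on staff departing from the paragraph that specifically governs the situation, and the dose count shows that the paragraph was not drafted with the alternatives in mind.

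Three stronger readings are tempting and are not supported:

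- A reader might infer that ciprofloxacin is imposed on every subject, or on everyone who withdraws before discharge. It is not. The regular course has alternatives, and the branch for subjects who stay names no drug.
- A reader might infer that departing subjects will be handled in haste, with serious consequences. The documents say nothing of staff time at departure and give no basis for predicting a serious outcome.
- A reader might want a count of affected subjects. The documents give neither an allergy rate nor a withdrawal rate, so none can be derived.

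**Conclusion.** Wrong as written: an internal contradiction that bears on patient safety and should be corrected. It is confined to challenged subjects who both leave at once on withdrawing and are allergic to ciprofloxacin or unwilling to take it. At most 30 subjects are challenged, and both conditions must coincide in one person. That the group will be very small is my expectation, not a figure from the documents. The finding does not depend on that expectation: it rests on exclusion 20 admitting such a subject and on Section 9.3.8 containing no exception. It has no bearing on the statistical results.

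**What to change.** The sponsor and investigator should reconcile the immediate-withdrawal text in Section 9.3.8 with Sections 7.3.2, 9.3.7 (exclusion 20) and 9.4.8.2, so that all give the same answer for a subject who is allergic to ciprofloxacin or unwilling to take it. Which regimen applies is for them to decide.

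Replacing the Section 9.3.8 text with a bare cross-reference to Section 9.4.8.2 would lose content. Only Section 9.3.8 provides an immediate withdrawer with a dose before departure and the remaining doses to take home. Section 9.4.8.2 contains neither provision, and the dispensing of remaining doses in Section 9.5.6.3 is written for participants discharged early under the discharge procedures. The revision should keep what Section 9.3.8 already provides.

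The cost is about one sentence, made through the amendment process in Section 11.1. No change is needed to the SAP, the data collected for the endpoints or the sample size.

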8.2.3 Secondary Safety endpoints

- Adverse events leading to study withdrawal
- Serious adverse events (SAEs) occurring during the 6 months of the study (from the time of challenge)

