9.5.2.1.5 Collecting and recording of AEs

AEs identified using any of the following methods will be recorded:

- AEs spontaneously reported by the subject
- AEs observed by the Investigator or medical personnel
- AEs elicited based on non-leading questions from the Investigator or medical personnel

AE collection starts with the administration of the challenge strain and continues until 28 days after challenge (Day 29). At the phone call approximately 6 months after challenge, the AE collection will be limited to Adverse Events of Special Interest (AESIs), SAEs and new chronic illnesses (see Section 9.5.6.5). Any AE with start on Day 1 from the time of challenge, must be recorded with date with/or without start time.

All AEs, serious and non-serious, should be recorded in the CRFs.

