9.5.2.1.7 Follow-up of AEs/SAEs

In general, AEs and expected events must be followed up until resolution or stabilization. AEs will be recorded for 28 days after challenge, SAEs and AESIs for 6 months after challenge. At the follow-up visit (Day 29), information on new AEs/SAEs, if any, and stop dates for previously reported ongoing AEs must be recorded. At the follow-up contact approximately 6 months after challenge, information on new SAEs, if any, and stop dates for previously reported ongoing AEs must be recorded.

It is the responsibility of the Investigator to follow-up on all SAEs until the subject has recovered, stabilized, or recovered with sequelae, and to report to SBH all relevant new information using the same procedures and timelines as those for the initial report. Relevant information includes discharge summaries, autopsy reports, and medical consultation. SAEs spontaneously reported by a subject to the Investigator within 30 days after the last follow-up assessment should be reported to SBH even after the clinical study has been finished, if, in the judgment of the Investigator, there might be an association between the event and the previous use of the test product or as a result of the investigation procedures.

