9.5.6.4 Out-patient follow-up Visit (Day 29 ± 4 days)

Procedures this day will include:

- Vital signs (temperature, pulse and blood pressure) will be measured
- Urine β-HCG pregnancy test for people of childbearing potential
- Medical interview and review of concomitant medications and AEs/AESIs/SAEs
- Focused Physical exam if participants have complaints/AEs or symptoms

- Collect blood and fecal samples for immunogenicity endpoints (exploratory)

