9.5.6.8 Early Termination Visit

If a subject terminates the study before Day 29, every effort will be made to have the subject undergo the procedures as described in Section 9.5.6.4 for the follow-up visit.

In case an early termination visit as described above is not possible, a follow-up safety phone call should be made as soon as possible after termination to capture any SAEs or AESIs since the last study visit, if possible.

The reason for premature termination must be documented in the subject's medical records and in the eCRF.

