## 7.4. Adverse Events, Serious Adverse Events and Other Significant Adverse Events

When calculating the incidence of adverse events (i.e., on a per subject basis), each subject will only be counted once and any repetitions of adverse events within a subject will be ignored; the denominator will be the total population size. All adverse events reported will be included in the summaries and analyses.

The following summaries for unsolicited adverse events will be presented by MedDRA system organ class and preferred term:

- Overall summary of adverse events ([Table 21](#));
- Summary of unsolicited adverse events ([Table 25](#));
- Summary of unsolicited AEs by severity and relationship to study product ([Table 26](#));
- Summary of AEs leading to study withdrawals ([Table 27](#));
- Listing of subjects with solicited events ([Listing 11](#));
- Listing of unsolicited AEs ([Listing 12](#));
- Listing of SAEs ([Listing 13](#));
- Bar charts of frequency and incidence of related AEs ([Figure 6, Figure 7](#));
- Bar charts of frequency and incidence of unsolicited AEs ([Figure 8, Figure 9](#)).

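### The fallback phone call for early terminators who cannot attend asks only about SAEs and AESIs, so non-serious AEs due through Day 29 are not actively sought

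*Protocol*

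**What the plan says.** **The general AE rule.** Protocol 9.5.2.1.5 runs AE collection from challenge to Day 29 and adds: "All AEs, serious and non-serious, should be recorded in the CRFs". Section 9.5.2.1.7 repeats the windows: "AEs will be recorded for 28 days after challenge, SAEs and AESIs for 6 months after challenge". It also requires AEs, as a general rule, to be followed until they resolve or stabilize.

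**The first route for early terminators.** Sections 9.3.8 and 9.5.6.8 tell the site to make every effort to carry out the Day 29 procedures. Those procedures (9.5.6.4) include "Medical interview and review of concomitant medications and AEs/AESIs/SAEs", which is a full AE review.

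**The fallback.** If that visit is not possible, 9.3.8 provides a call "as soon as possible after termination to capture any SAEs or AESIs since the last study visit". Section 9.5.6.8 says the same: "a follow-up safety phone call should be made as soon as possible after termination to capture any SAEs or AESIs". Neither section mentions non-serious AEs or AEs still open.

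**The analysis.** For AE incidence, SAP 7.4 states that "the denominator will be the total population size". SAP 3.5 plans no imputation. One of the two secondary safety endpoints (protocol 8.2.3) is "Adverse events leading to study withdrawal".

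**The concern.** The protocol sets one window for all AEs, then gives one group of subjects a contact that covers only part of what is due in that window. The SAP does not make up the difference. The subject stays in the denominator, and a non-serious AE that nobody asked about appears in the tables as no event.

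The stake is the completeness of the non-serious AE data: the overall AE summary and the unsolicited-AE tables (SAP Tables 21, 25 and 26, numbered as in SAP 7.4). With 25 to 30 subjects, a single event moves a percentage visibly.

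Two features make the gap more than theoretical:

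- **Antibiotic-related AEs.** A subject who withdraws immediately leaves with most of the antibiotic course still to take (9.3.8). Protocol 7.3.2 reports gastrointestinal side effects of ciprofloxacin in as many as 5 in 100. The protocol asks for causality against antibiotics, and SAP Table 21 has rows for antibiotic-related unsolicited AEs. Non-serious events of this kind could fall in the unasked interval.
- **Comparison with the six-month contact.** That contact must record stop dates for ongoing AEs (9.5.2.1.7) and follow up open ones (9.7.3.1). The fallback call is made for subjects who stop inside the AE window, yet on ongoing AEs it asks less than a contact made about five months after that window closes. This looks like an oversight in drafting, not a choice.

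**Working it through.** The documents give no figure for AE capture in early terminators, so there is nothing to reproduce. The check compares the text and then illustrates the size.

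**1. Scope of each contact**

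| Contact | Source | Non-serious AEs since last visit | Ongoing AEs | SAEs and AESIs |
|---|---|---|---|---|
| Day 29 visit | Protocol 9.5.6.4, 9.5.2.1.7 | yes | yes (stop dates) | yes |
| Fallback call before Day 29 | Protocol 9.3.8, 9.5.6.8 | not stated | not stated | yes |
| Six-month contact | Protocol 9.5.2.1.5, 9.5.2.1.7, 9.7.3.1 | no (outside the AE window) | yes (stop dates) | yes |

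No section of the protocol or SAP extends the call to all AEs, and none says that the AE window ends at termination.

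**2. Length of the unasked interval**

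- During the in-patient stay AEs are recorded daily (9.5.6.2.3) and again at discharge (9.5.6.3). For a subject who stops on leaving the unit, the gap is short.
- Routine discharge is on Day 9, the extra visits for early-discharged subjects fall on Days 7 and 8 (9.5.6.7), and the next scheduled contact is Day 29.
- A discharged subject who terminates as late as Day 28 has gone 28 − 9 = 19 days since a Day 9 discharge, or 28 − 8 = 20 days since a Day 8 visit. The upper end is therefore just under three weeks.

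**3. Effect on an incidence**

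Inputs: 25 to 30 subjects challenged (protocol section 9), total population as denominator (SAP 7.4), no imputation (SAP 3.5), Clopper-Pearson intervals (SAP 3.1.1).

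If *m* subjects each have their only event of a given type missed, the reported incidence falls by *m*/N:

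- N = 25: 1/25 = 4.0 points per subject
- N = 30: 1/30 = 3.3 points per subject

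Exact 95% limits for *x* events in N are the 2.5% quantile of Beta(*x*, N − *x* + 1) and the 97.5% quantile of Beta(*x* + 1, N − *x*); the lower limit is 0 when *x* = 0.

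| N | One true case | Recorded as none |
|---|---|---|
| 25 | 4.0% (0.1 to 20.4) | 0% (0 to 13.7) |
| 30 | 3.3% (0.1 to 17.2) | 0% (0 to 11.6) |

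The value of *m* is not given. If 0 to 2 is assumed, the understatement for one event type is 0 to 2/25 = 8.0 points with 25 subjects, or 0 to 2/30 = 6.7 points with 30. That range shows scale and is not a forecast.

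**4. Route to the withdrawal-AE endpoint**

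- The primary reason for stopping must be entered in the eCRF (9.3.8; 9.5.6.8 repeats the duty to document the reason).
- SAP Listing 3 carries the AE number in the reason column, and Listing 12 has a column for discontinuation due to the AE.
- SAP Table 21 counts AEs leading to early termination from the AE eCRF, and Table 27 tabulates them by MedDRA term. Both need an AE record.

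The endpoint therefore loses a case only if a contributing AE is neither given as the reason nor entered on the AE form.

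**The case against.** A reader might infer that subjects who terminate early are the ones who supply the withdrawal-AE endpoint, that their AEs go uncollected, and that the endpoint is therefore biased downward by rule. The documents do not support this, for three reasons.

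- An AE that makes a subject stop would normally be known when the subject stops. The reason is mandatory in the eCRF and the SAP links it to the AE record. Losing such a case would ordinarily mean that site staff did not follow the recording rules.
- The groups do not coincide. The narrow call applies only after efforts to arrange the full visit have failed, and to terminations for any reason, including non-compliance. A subject who withdraws for an AE and attends gets the complete review. One who leaves the unit but agrees to return is not counted as terminated at all (9.3.8, 9.5.6.7).
- Missed is too strong a word. AEs recorded up to the last visit are kept, spontaneous reports are still recorded (9.5.2.1.5), and the general duty to follow AEs remains. AESIs include continuing gastrointestinal conditions, so the call already asks about lasting sequelae of the challenge.

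All of this stands, and it confines the point to non-serious AEs not actively sought after the last visit. It does not remove the point, because nothing in the documents gives the call the scope of the AE rule it stands in for. The reason field holds one primary reason, so an AE that merely contributed to stopping, and began after the last visit, could still escape.

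A practical objection also stands. The call is to be made as soon as possible after termination, so it cannot collect AEs with onset up to Day 29 however it is worded. A subject who cannot be reached gains nothing from a wider call.

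**Conclusion.** The point holds as a minor inconsistency in AE collection. The fallback call is narrower than the protocol's own rule, and the SAP counts the uncollected part as no event.

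Non-serious AE incidence can be understated by 4.0 points (N = 25) or 3.3 points (N = 30) for each subject whose only event of that type is missed. This assumes that the subject terminated before Day 29, could not attend, had a non-serious event after the last visit and did not report it unprompted. The documents give no expected number of such subjects, and it may be zero.

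The effect on the withdrawal-AE endpoint is conditional, as set out in step 4 of the working; the figures above should not be read as an expected bias in that endpoint. By its wording the call covers SAEs and AESIs. The primary endpoint does not depend on this contact.

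**What to change.** **Protocol 9.3.8 and 9.5.6.8.** Reword the content of the call so that it collects, since the last study visit, all AEs whether serious or not, the current status of any AE still open, and any SAEs or AESIs.

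**Same two sections.** State that for these subjects AE observation ends at the call, or at the last visit if the call is not achieved. This is needed because an early call cannot cover the time to Day 29.

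**SAP Listing 3.** Add the study day on which AE observation ended. SAP Table 10 already counts early terminations and Day 29 completers, and Listing 3 has a study-day column, but neither shows how far AE review reached for each subject.

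**Cost.** One or two sentences in two protocol sections, through a written amendment (11.1), and one column in a listing. The call is already planned and becomes slightly longer. No extra visit, contact or sample is needed, and no analysis method changes.
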